9 DATA MANAGEMENT

As used in this protocol, the term CRF should be understood to refer to either a paper form or an electronic data record or both, depending on the data collection method used in this study.

For this study subject data will be entered into an electronic CRF using a validated data system.

9.1 Source Documents/ Data

The source documents, such as diary cards, which contain the source of data recorded in the CRF should be specified in Section 6. The CRF can be used as a source document at the discretion of data management.

Each subject will be assigned and identified by a unique Screening Number. Any reference made to an individual subject within the study must be done using the unique Screening Number.

9.2 Case Report Form

A CRF is a printed, optical, or electronic document designed to record all of the protocol required information to be reported to the sponsor on each trial subject. Refer to the appropriate CRO handbook and study-specific CRF specifications.

For each subject who has given informed consent/assent and has been screened, CRF must be completed and signed by the Principal Investigator (or authorized designee) to certify that the data are complete and correct.

Management of clinical data will be performed in accordance with Third Party Biostatistics and Data Management vendor applicable standards and data cleaning procedures with oversight by GSK CH to ensure integrity of the data e.g., removing errors and inconsistencies in the data.

GlaxoSmithKline Consumer Healthcare Confidential
Template Version Effective: 22-Jun-2017

 GlaxoSmithKline	Document Name	208-208_166-clinical-protocol.docx		
	Type	Version	Document Identifier	Effective Date
	eldo_controlled	0.0: Effective	090032d580267d09	07-Nov-2017 10:31:16
	Reason For Issue	Auto Issue		

Sodium fluoride and potassium nitrate
208166
Clinical Protocol, 08 Aug 2017

In order to protect the privacy of subjects, no Personally Identifiable Information (PII) (including the subject's name or initials or full birth date) is to be recorded in the CRF or as part of the query text.

All CRF pages should be completed during a subject assessment when the CRF has been designated as the source. Data that is sourced elsewhere should be entered into the CRF in an agreed upon timeframe between the Investigator and Sponsor.

GSK CH will obtain and retain all CRFs and associated study data at the completion of the study.

9.3 Data Handling

Documentation of all data management activities should allow step-by-step retrospective assessment of data quality and study performance.

Any changes or corrections to data will be performed in the Electronic Data Capture (EDC) System, and it will include rationale for changes. The EDC system has an audit trail, which will provide a complete record of the changes and corrections endorsed by the Investigator.

Adverse events will be coded using MedDRA (Medical Dictionary for Regulatory Activities) and concomitant medications terms (if applicable) using an internal validated medication dictionary, GSKDrug.

9.3.1 Queries

Programmed edit checks will be generated automatically, as the data is being entered into the system. Data Management will also run reports and listings on the CRF data, in addition to the queries already programmed and generated by the system, to raise manual queries as needed for site clarification or correction. The Clinical Dictionary Development and Management Group will raise queries as needed on safety data to code the terms (Adverse Events and Drugs) appropriately.

The study monitor at the study site will review the CRFs in accordance with the monitoring plan, and any queries will be generated in the EDC System to the Investigator or designee, enabling the errors to be addressed in parallel with Data Management review. The study monitor can also run reports and listings on the CRFs, to raise manual queries as needed for site clarification or correction.

9.4 Processing Patient Reported Outcomes

Patient reported outcome (PRO) data may be collected from diary cards, questionnaires, etc, and entered into the sponsor's clinical data management system (DMS). In instances where the PRO data is entered into the DMS by GSK CH, the PROs will be anonymized as agreed and documented prior to study initiation. PROs that are source will be retained by the investigator and certified copies will be sent to GSK CH.

 GlaxoSmithKline	Document Name	208-208_166-protocol.docx		
	Type	Version	Document Identifier	Effective Date
	eldo_controlled	0.0: Effective	090032d580267109	07-Nov-2017 10:31:16
	Reason For Issue	Auto Issue		

Sodium fluoride and potassium nitrate
208166
Clinical Protocol, 08 Aug 2017

In order to protect the privacy of subjects, no Personally Identifiable Information (PII) (including the subject's name or initials or birth date) is to be recorded on all PRO's that will be forwarded to GSK CH.

9.5 External Data

External Data are subject data obtained externally to the CRF. These data are generated from laboratory instruments, computers or other sources and then transcribed into a file and format agreed upon by GSK CH to identify the subject and time point referenced in the CRF and/or protocol.

An agreed upon quality control process is performed against the transcribed data to the source to ensure the accuracy of the transcription. The transcribed data is transmitted in an agreed upon format to GSK CH.

Reconciliation will be performed between the transcribed data and the clinical database to ensure subject and time point referenced in the Clinical Database.

10 STATISTICAL CONSIDERATIONS AND DATA ANALYSES

The endpoints of this study are described below and in Section 10.2

Primary end point:

%SMHR

The extent of remineralization will be calculated as the % recovery in SMH, which is calculated from the enamel indentation length at baseline, after the first erosive challenge and after the *in situ* remineralization phase after 4 hrs of intraoral phase.

Secondary end point:

%RER

This end point aims to test whether the formulations prevents enamel demineralization after the 4 hours intra oral remineralization phase as per a second erosion challenge. The %RER is calculated based on the indentation length at baseline, after the first and the second erosive challenge after 4 hrs.

EFU

EFU is assessed by the microdrill enamel biopsy, and its determined after 4 hours *in situ* remineralization period but before the second extra-oral erosive challenge. This measurement will provide with micrograms of fluoride per square centimeter ($\mu\text{g F/cm}$).

 GlaxoSmithKline	Document Name	208-208_166-oral-protocol.docx		
	Type	Version	Document Identifier	Effective Date
	eldo_controlled	0.0: Effective	090032d580262109	07-Nov-2017 10:31:16
	Reason For Issue	Auto Issue		

Sodium fluoride and potassium nitrate
 208166
 Clinical Protocol, 08 Aug 2017

Exploratory end point:

%SMHR, %RER and EFU after 2 hours of intraoral exposure will be evaluated as exploratory end point.

The ARR measures acid resistance of the treated enamel after 2 and 4 hours intraoral phase. It is calculated based on the indentation length after the second erosive challenge and the *in situ* remineralization phase, and after the first erosive challenge and baseline.

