1.2 Background and Rationale

Justification and need to perform the study

The experimental formulation tested in this study is based on the currently marketed Sensodyne Pronamel dentifrice and tested *in vitro* for a superior performance. In order to support the experimental dentifrice market introduction in the US, an *in situ* investigation comparing the experimental dentifrice with a fluoride free placebo dentifrice (primary objective) and with a relevant marketed dentifrice is needed (secondary objective) to investigate the efficacy in enhancing remineralization and preventing demineralization. Therefore, the aim of this study is to investigate the performance of an experimental dentifrice formulation in promoting enamel remineralization and inhibiting post-treatment enamel demineralization in an *in situ* erosion model, in comparison with a fluoride-free placebo and with a marketed competitor dentifrice product.

The *in situ* model to be used in this study has been extensively used to investigate the performance of the currently marketed Sensodyne Pronamel in previously published studies (Barlow et al 2009) and other GSK CH studies (CCI [REDACTED], [REDACTED], GSK-Z3480664, CCI [REDACTED], GSK-Z6961385).

Study and dose rationale

This clinical investigation will use a previously published *in situ* remineralization model (Barlow et al 2009) which consists of placing pre-eroded sterilized bovine enamel specimens intra orally using a palatal appliance and testing the enhancement of remineralization and prevention of demineralization performance of the experimental formulation after 2 and 4 hours post treatment application based on surface micro hardness measurements. Details of enamel and palatal appliance preparations are specified in protocol Section 7.3. The palatal appliances (Figure 1) will be made for each eligible subject, and each will carry two plastic holders containing a total of eight bovine enamel specimens (four in each holder).

GlaxoSmithKline Consumer Healthcare Confidential
 Template Version Effective: 22-Jun-2017

Document Name	208-208_166-clinical-protocol.docx		
Type	Version	Document Identifier	Effective Date
eldo_controlled	0.0: Effective	090032d580262109	07-Nov-2017 10:31:16
Reason For Issue	Auto Issue		

Sodium fluoride and potassium nitrate
208166
Clinical Protocol, 08 Aug 2017

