2 STUDY OBJECTIVES AND ENDPOINTS

Table 2-1 Study Objectives and Endpoints

Objective(s)	Endpoint(s)
Primary	
To investigate the efficacy of an experimental dentifrice containing 1150 ppm fluoride and 5% KNO ₃ to enhance remineralization of enamel relative to a fluoride free placebo dentifrice.	%SMHR after 4 hrs intraoral phase following a single exposure.
Secondary	
Efficacy	
To investigate the efficacy of an experimental dentifrice containing 1150 ppm fluoride and 5% KNO ₃ to inhibit demineralization of enamel relative to a fluoride free placebo dentifrice.	%RER after 4 hrs intraoral phase following a single exposure.
To investigate the efficacy of an experimental dentifrice containing 1150 ppm fluoride and 5% KNO ₃ to promote fluoride uptake in enamel relative to a fluoride free placebo dentifrice.	EFU after 4 hrs intraoral phase following a single exposure.
To investigate the efficacy of an experimental dentifrice containing 1150 ppm fluoride and 5% KNO ₃ to enhance remineralization, to inhibit demineralization and to promote fluoride uptake in enamel relative to a benchmark comparator containing 1100 ppm fluoride (Crest Pro Health).	%SMHR, %RER and EFU after 4 hrs intraoral phase following a single exposure.
Safety	
To evaluate the oral tolerance of an experimental dentifrice containing 1150 ppm fluoride and 5% KNO ₃ following a single brushing event.	Proportion of treatment emergent oral adverse events post 4 hours intraoral exposure.
Exploratory	
To make all paired comparisons of the efficacy of an experimental dentifrice containing 1150 ppm fluoride and 5% KNO ₃ after 2 hours of intraoral exposure to enhance remineralization of enamel, to inhibit demineralization of enamel and to promote fluoride uptake in enamel.	%SMHR, %RER and EFU after 2 hrs intraoral phase following a single exposure.
To characterize the efficacy of the experimental dentifrice containing 1150 ppm fluoride and 5% KNO ₃ ; the fluoride free placebo; and the benchmark comparator containing 1100 ppm (Crest Pro Health) after 2 and 4 hours of intraoral exposure on resistance to acid challenge.	Summary statistic table of ARR after 2 and 4 hrs intraoral phase.

Abbreviations: SMHR: Surface micro hardness recovery, RER: Relative erosion resistance, EFU: Enamel fluoride uptake, ARR: Acid resistance ratio

GlaxoSmithKline Consumer Healthcare Confidential
Template Version Effective: 22-Jun-2017

Document Name	208-208_166-palataprotocol.docx		

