Type	Version	Document Identifier	Effective Date
eldo_controlled	0.0: Effective	090032d580262109	07-Nov-2017 10:31:16
Reason For Issue	Auto Issue		

Sodium fluoride and potassium nitrate
208166
Clinical Protocol, 08 Aug 2017

This study will be considered successful if the experimental dentifrice demonstrates a statistically significant enhancement of remineralization, as measured by %SMHR in comparison with the placebo dentifrice after 4 hours intraoral phase.

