3 STUDY DESIGN AND SUBJECT POPULATION

This will be a randomized, controlled, single center, single- blind (to the dental examiner and specimen analysts), 3 period, 3 treatment, cross-over, *in situ* design which consists of placing pre-eroded bovine enamel specimens intra orally using a palatal appliance and testing the remineralizing performance of the experimental, comparator and placebo dentifrices 2 and 4 hours post treatment application, based on surface micro hardness measurements. This study will be carried out in healthy adults with a maxillary dental arch suitable for the retention of the palatal appliance. A sufficient number of healthy subjects will be screened so that up to 66 subjects are randomized to participate in the study to ensure 60 evaluable subjects complete the entire study. Subjects will be recruited from an existing panel of subjects pre-fitted with a palatal appliance (IRB approved panel CCI [REDACTED]). For a subject whose appliance does not fit adequately and for whom adjustment of the appliance is not sufficient to obtain proper fit, the subject may have a new appliance made. Surface microhardness (SMH) measures changes in the mineral content of enamel, and is used to calculate surface micro hardness recovery (%SMHR), relative erosion resistance (%RER) and acid resistance ratio (ARR). Fluoride uptake of the experimental dentifrice will be assessed by enamel fluoride uptake (EFU) measurements. For each treatment and subject these measurements will be performed on the same enamel specimen, in the four replicates for each time point. The erosive acid challenge, with a commercially available grapefruit juice, will be carried out *ex vivo* and therefore does not pose a risk to the subject's teeth. The overall study design sequence of events is sketched in Figure 2.

For the aim of this study, a fluoride-free placebo dentifrice will be used as comparator to establish if the fluoride present in the experimental dentifrice can provide and enhancement of remineralization and prevention of demineralization in this *in situ* model. Additionally, a relevant commercially available dentifrice containing 1100 ppm fluoride (as stannous fluoride, SnF₂) will be used as a comparator (secondary objectives) to investigate the superior performance of the experimental dentifrice in enhancing remineralization and preventing demineralization.

	Document Name	208-208_166-clinical-protocol.docx		
	Type	Version	Document Identifier	Effective Date

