10.1 Sample Size Determination

A sufficient number of healthy subjects will be screened so that up to 66 subjects are randomized to participate in the study to ensure 60 evaluable subjects complete the entire study. With a sample size of 60 subjects that complete the study, the study will have 90% power to detect a difference in means of 5.0 in %SMHR at 4 hours, assuming a standard deviation of differences of 11.92 (estimated from GSK study Z2560490, which was a study of similar design), using a paired t-test with a 0.05 two-sided significance level.

A sample size of 60 subjects will be large enough to also detect a difference of 7.4 in RER with 80% power.

A sufficient number of healthy adult subjects will be selected from the Oral Health Research Institute’s IRB approved database of previous research studies or from persons expressing interest in participating in research, and screened for participation.

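### A significant %RER shows better net erosion resistance but does not by itself show less softening at the second acid challenge, and ARR, the only variable containing that softening, has no planned treatment difference or confidence interval

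*Protocol*

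**What the plan says.** Section 1.2 names two aims for the experimental dentifrice: "promoting enamel remineralization and inhibiting post-treatment enamel demineralization". Table 2-1 gives them separate objectives. Remineralization is tied to %SMHR at 4 hours (primary). The ability "to inhibit demineralization of enamel relative to a fluoride free placebo dentifrice" is tied to %RER at 4 hours (secondary), and a further secondary objective repeats this against the marketed comparator. Section 10 explains that %RER "aims to test whether the formulations prevents enamel demineralization after the 4 hours intra oral remineralization phase as per a second erosion challenge".

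Section 10 also says: "The ARR measures acid resistance of the treated enamel after 2 and 4 hours intraoral phase". In Table 2-1, however, the endpoint for that variable is "Summary statistic table of ARR after 2 and 4 hrs intraoral phase", and section 10.2.5 likewise plans only summary statistics by treatment and time point. The ANOVA, pairwise differences and 95% CIs are specified for %SMHR, %RER and EFU.

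Section 3 states: "For each treatment and subject these measurements will be performed on the same enamel specimen". Success is defined on %SMHR alone: "This study will be considered successful if the experimental dentifrice demonstrates a statistically significant enhancement of remineralization, as measured by %SMHR".

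**The concern.** The %RER formula compares the indentation after the second challenge (E2) with that after the first (E1). It does not contain R, the state of the enamel when the second challenge begins. Softening during that challenge, E2-R, enters only ARR. A dentifrice that remineralizes more but softens just as much at the second challenge therefore still shows a higher %RER.

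At stake is how two secondary results are read, versus placebo and versus the marketed comparator. Each could be described as an effect on demineralization over and above remineralization when the %SMHR gain explains all of it. The output that would separate the two, an ARR difference with an interval, is not planned.

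**Working it through.** **Inputs.** With B the baseline indentation length:
- %SMHR = 100(E1-R)/(E1-B), section 10.2.2.
- %RER = 100(E1-E2)/(E1-B), section 10.2.3.
- ARR = 1-(E2-R)/(E1-B), section 10.2.5.
- Preselection at B = 43 µm and E1 = 120 µm (mid-range values), section 10.2.2.
- Section 10.1: 60 completers; %SMHR difference 5.0, SD of differences 11.92, 90% power, paired t-test, two-sided 0.05. For the second variable: "A sample size of 60 subjects will be large enough to also detect a difference of 7.4 in RER with 80% power".

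**The plan's own figure.** Paired-t power (noncentral t) for 5.0 with SD 11.92 and n = 60 is 89.2%; the normal approximation gives 90.1%. The stated 90% is reproduced.

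**Identity.** E1-E2 = (E1-R)-(E2-R). Dividing by (E1-B) and multiplying by 100:

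%RER = %SMHR - 100(1-ARR)

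It holds per specimen. Averaging over specimens and taking treatment differences are linear, so:

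difference in %RER = difference in %SMHR + 100 × difference in ARR

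This is exact with complete, untransformed data. With dropout or missing E2 readings, separately fitted mixed models make it approximate. In simulation with 66 subjects, 6 of whom lost period 3, the median gap was 0.05 points and the maximum 0.54 (assumed correlation 0.7, between-subject SD 10). It does not carry over to the transformation or rank fallback in 10.2.2 and 10.2.3.

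**Illustration** (B = 43, E1 = 120, so E1-B = 77; the R and E2 values are assumed). Placebo R = 100 gives %SMHR 20/77 = 26.0; test R = 96.15 gives 23.85/77 = 31.0.
- Equal softening of 20 µm: ARR = 1-20/77 = 0.740 in both arms. %RER is 0.0 v (120-116.15)/77 = 5.0. The whole %SMHR gain reappears in %RER.
- Equal E2 of 120 µm: %RER is 0.0 in both arms. ARR is 0.740 v 1-23.85/77 = 0.690, so ARR disfavours the better remineralizer.

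**Chance of a significant %RER with no ARR difference.** Solving 80% power for 7.4 with n = 60, on the same paired t-test, gives an SD of RER differences of 20.12. The %RER difference then equals the %SMHR difference:

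| %SMHR difference | Power, SD 20.12 | SD 15 | SD 25 |
|---|---|---|---|
| 5.0 | 47% | 72% | 33% |
| 7.4 | 80% | 96% | 62% |
| 10 | 97% | 99.9% | 86% |

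SDs of 15 and 25 are assumed, to show the range. %RER p-values are presented only if the primary comparison is significant. For the placebo comparison at 5.0, SD 20.12, the chance that both are significant is therefore at least 0.473 + 0.892 - 1 = 0.365 and at most 0.473. At 7.4 and 10 the condition hardly matters, because %SMHR power exceeds 99%.

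**What the planned outputs give on ARR.** The point difference can be recovered as (difference in %RER - difference in %SMHR)/100. Its interval cannot, because it depends on rho, the within-subject correlation of the two differences, which is not a planned output. On the 100 × ARR scale, SD² = 20.12² + 11.92² - 2·rho·20.12·11.92 and half-width = 2.001 × SD/√60:
- rho 0.9: SD 10.7, half-width 2.8 points.
- rho 0.5: SD 17.5, half-width 4.5 points.

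Across the same correlations, the range is 1.7 to 3.5 points at SD 15 and 3.9 to 5.6 at SD 25.

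**The case against.** The strongest reply is that nothing stated is wrong. %RER is openly defined, and section 10 lists the three readings it uses, so the absence of R is plain. No sentence claims that %RER isolates demineralization from remineralization. The introduction itself links the two, describing remineralization as ideally yielding mineral that better resists later acid. Hardness retained after re-challenge is then a legitimate target, and a significant %RER meets the objective as Table 2-1 sets it. All of this stands.

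A reader might go further and infer that %RER is invalid, or that the secondary objectives would be falsely declared met. The documents support neither. A reader might also divide 5.0 by 7.4 to get the share of %RER due to remineralization. That ratio sets a 90%-power detectable difference against an 80%-power one, and neither is a forecast, so it measures no such share.

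It is also fair that ARR is not a neutral yardstick (second illustration), that the point difference is recoverable, that an ARR interval may be inconclusive, and that the analysis plan, not shown, could add one. What remains is that the protocol itself assigns ARR a summary table while naming it the measure of acid resistance, and that subtraction does not yield a paired interval.

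**Conclusion.** The point holds as a matter of interpretation, with low severity. A significant %RER supports a better net position after remineralization plus re-challenge. Alone, it does not show that enamel softened less at the second challenge. With equal ARR in both arms, %RER would be significant about 47%, 80% or 97% of the time at %SMHR differences of 5.0, 7.4 or 10. At the planned primary effect of 5.0 that is slightly less than an even chance.

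The identity rests only on the protocol's formulas and on all readings coming from the same specimens. The probabilities also rest on the back-calculated SD of 20.1 and on the 7.4 having been derived with the same test and alpha as the primary. The primary endpoint, the sample size for it and the success criterion are untouched.

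**What to change.** - In 10.2.5 and Table 2-1, analyse 4-hour ARR with the ANOVA already specified (period and treatment fixed, subject random). Report pairwise differences with 95% CIs as exploratory support.
- In section 10 and 10.2.3, state that %RER is interpreted as net erosion resistance (remineralization plus acid resistance), read together with the %SMHR and ARR differences.
- Keep %RER as the secondary endpoint, and do not draw the conclusion from ARR alone.

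The cost is some wording and one more run of an existing model on a variable already calculated. It needs no new subjects or measurements and no alpha. The downsides are a narrower demineralization claim and an ARR interval with no planned power, which may settle little at the half-widths shown above.
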